5.3 Treatment assignment and randomization

At Baseline (Visit 101), all eligible patients will be randomized via Interactive Response Technology (IRT) to one of the treatment arms in the double-blind Treatment epoch and to one of the treatment arms in the double-blind Treatment withdrawal epoch. Logistically, the randomization into all epochs will be pre-specified according to the following randomization scheme.

Table 5-1 Randomization scheme

Treatment epoch (treatment arms)	Treatment withdrawal epoch (treatment arms)	Randomization ratio
Placebo b.i.d.	Placebo b.i.d.	2
EMA401 100 mg b.i.d.	EMA401 100 mg b.i.d.	1
EMA401 100 mg b.i.d.	Placebo b.i.d.	1

The investigator or his/her delegate will contact the IRT after confirming that the patient fulfills all the inclusion/exclusion criteria. The IRT will assign a randomization number to the patient, and will specify a unique medication number for the first package of study drug to be dispensed to the patient. The randomization number will not be communicated to the caller.

At Week 12 (Visit 199), all patients who completed the 12-week double-blind Treatment epoch will enter the 1-week double-blind Treatment withdrawal epoch. The IRT system will indicate the unique medication number for the package of study drug to be dispensed to the patient during the double-blind Treatment withdrawal epoch. This medication number will correspond to the blinded withdrawal regimen assigned at Baseline.

The randomization numbers will be generated using the following procedure to ensure that treatment assignment is unbiased and concealed from patients and investigator staff. A patient randomization list will be produced by the IRT provider using a validated system that automates the random assignment of patient numbers to randomization numbers. These randomization numbers are linked to the different treatment arms, which in turn are linked to medication numbers. A separate medication list will be produced by or under the responsibility of Novartis Drug Supply Management using a validated system that automates the random assignment of medication numbers to packs containing the investigational drug(s).

Randomization will be stratified by region (e.g. US, EU) and use of concomitant pain medication for PDN (yes/no) in order to achieve balance of treatment allocation within the stratification factors.

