9.4.2 Statistical model, hypothesis, and method of analysis

The aim is to estimate the treatment effect of the investigational drug (EMA401) compared to placebo, for the target population on the primary pain parameter. The definition and the justification of the corresponding primary estimand, as well as the definition of the supplementary and secondary estimands for NRS are detailed in an Estimand Charter. The definitions of the estimands for the key secondary variable NPSI will also be detailed in an Estimand Charter.

Summary statistics by treatment and visit will be provided for the primary and key secondary efficacy variables.

The primary estimation method for the both primary and key secondary efficacy variable will be based on an Analysis of Covariance (ANCOVA) model including region (e.g. US, EU), treatment, sex, use of concomitant pain medication for PDN (yes/no) as factors and baseline score of the corresponding scale and age as covariate in an univariate fashion. The analysis will account for different post-randomization events as follows:

- **Changes in doses of concomitant medication for PDN:** Efficacy observations collected during the period of changes in doses of concomitant medication for PDN (compared to baseline) and the 3-days thereafter will be excluded, since they are considered affected by the concomitant medication dose change. The resulting missing data after this step will be imputed via multiple imputation method using the Missing at random (MAR) assumption.
- **Intake of rescue medication:** Efficacy data collected during intake of rescue medication will be used for analysis.
- **Intake of prohibited medications with potential confounding effect prior to study treatment discontinuation:** The prohibited medications with a potential confounding effect are defined as those listed in [Table 5-2](#) requiring study treatment discontinuation. Efficacy observations collected during the intake period of such prohibited medications and the 7-days thereafter will be excluded, since they are considered affected by the prohibited medication intake. The resulting missing data after this step will be imputed via multiple imputation method using the MAR assumption.

The design feature of retrieved drop-outs, considered in order to minimize the occurrence of missing data on primary pain parameter, is exploited for the statistical analysis as follows:

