The primary analysis on the change from baseline to Week 12 in the weekly mean of the 24-hour average pain score will be performed as originally planned. Besides the primary estimand, which is of main clinical interest, the supplementary estimand, which provides insight into the magnitude of improvement in efficacy that might be achieved if all patients were able to take EMA401 as prescribed for 12 weeks, will be analysed. The other planned supplementary estimands will be dropped, as they are of minor interest in the situation with many study treatment discontinuations due to trial termination in the scope of the Urgent Safety Measures (USM).

To support the primary analysis and to get an idea about the effect that might be achieved if the trial had not been terminated and if all patients had the chance to complete the Week 12 assessment, a sensitivity analysis on a modified population will be performed. The modified full analysis set will include all patients who had a chance to complete the study before the termination date, i.e. who had been randomized at least 12 weeks before study termination date.

Similar considerations were made for the key-secondary endpoint.

Due to the considerably reduced number of patients who completed the study, only descriptive subgroup analyses will be provided. Moreover, the secondary endpoints will also be summarized descriptively only.

1 Introduction

This statistical analysis plan (SAP) describes all planned analyses for the Clinical Study Report (CSR) of study CEMA401A2202, a Phase 2, double-blind, placebo-controlled, randomized trial to determine the safety and efficacy of EMA401 in reducing 24-hour average pain intensity score in patients with painful diabetic neuropathy.

The content of this SAP is based on the final version of protocol CEMA401A2202 (release date 15-Sep-2017). All decisions regarding final analysis, as defined in the SAP document, have been made prior to database lock and unblinding of the study data.

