1.1 Study design

The study is interventional, randomized, parallel, placebo-controlled, double-blind treatment.

The study will consist of a Screening epoch (up to 4 weeks), a double-blind Treatment epoch (12 weeks), and a double-blind Treatment withdrawal epoch (1 week).

- Patients will be randomized in a 1:1 ratio to treatment with placebo or EMA401 100 mg b.i.d.

Overall approximately 400 patients will be enrolled in the study (i.e. approximately 200 patients will be enrolled in each treatment arm).

At Week 12 (Visit 199), all patients who completed the 12-week double-blind Treatment epoch will enter the 1-week double-blind Treatment withdrawal epoch. The IRT system will indicate the unique medication number for the package of study drug to be dispensed to the patient during the double-blind Treatment withdrawal epoch. This medication number will correspond to the blinded withdrawal regimen assigned at Baseline.

Randomization will be stratified by region (America, Europe and Australia) and use of concomitant pain medication for PDN (yes/no) in order to achieve balance of treatment allocation within the stratification factors.

[figure not shown]
Primary objective of this study is to compare the efficacy of EMA401 vs. placebo in 24-hour average pain intensity score at Week 12, using an 11 point Numeric Rating Scale (NRS) by testing the superiority of EMA401 100 mg b.i.d. vs. placebo.

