2.5.2 Statistical hypothesis, model, and method of analysis

The aim is to estimate the treatment effect of the investigational drug (EMA401) compared to placebo, for the target population on the primary pain parameter. The definition and the justification of the corresponding primary estimand, as well as the definition of the supplementary and secondary estimands for NRS are detailed in the Estimand Charter. The most recent version of the Estimand charter stored at [REDACTED] available before the database lock will be used as reference.

The primary estimation method is based on an Analysis of Covariance (ANCOVA) model including treatment, sex, use of concomitant pain medication for PDN (yes/no) as factors and age and baseline (mean pain intensity) score as covariate. The analysis will account for different intercurrent events (i.e. events that occur post-randomization) as follows:

- **Changes in doses of concomitant medication for PDN:** Efficacy observations collected during the period of changes in doses of concomitant medication for PDN (compared to baseline) and the 3-days thereafter will be excluded, since they are considered affected by the concomitant medication dose change. The resulting missing data after this step will be imputed via multiple imputation method using the Missing at random (MAR) assumption.
- **Intake of rescue medication:** Efficacy data collected during intake of rescue medication will be used for analysis.
- **Intake of prohibited medications with potential confounding effect prior to study treatment discontinuation:** The prohibited medications with a potential confounding effect are defined as those listed in Table 2-1 requiring study treatment discontinuation. A list of prohibited medications is available at the following [REDACTED] location

[REDACTED]. Efficacy observations collected during the intake period of such prohibited medications and the 7-days thereafter will be excluded, since they are considered affected by the prohibited medication intake. The resulting missing data after this step will be imputed via multiple imputation method using the MAR assumption.

Table 2-1 Prohibited medication

Medication	Prohibition period	Action taken for study treatment
Prohibited prior to Screening and throughout study		
Any skeletal muscle relaxant (e.g. baclofen, orphenadrine, methocarbamol)	2 weeks prior to Screening and after Screening	None
Mexiletine	2 weeks prior to Screening	None

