These patients must continue to adhere to protocol requirements (see respective protocol Table 6-2). The design feature of retrieved drop-outs, considered in order to minimize the occurrence of missing data on primary pain parameter, is exploited for the statistical analysis as follows:

- **Permanent discontinuation of study treatment due to AE, lack of efficacy (LoE) and use of prohibited medication:** If retrieved drop-out data are available, these will be used for analysis. If no data was retrieved after study treatment discontinuation, missing data will be multiply imputed based on placebo arm data, i.e. “jump to reference” (J2R) assumption for the EMA401 arm, missing at random assumption for placebo arm (Carpenter, Roger, and Kenward 2013). Of note, alternatively one could build the imputation model based on the RDO data, however, we expect sparse RDO data which will likely hinder us to build an imputation model. More details on the imputation model are specified in Section 5.
- **Permanent discontinuation of study treatment due to other reasons than AE, LoE and use of prohibited medication (including discontinuation due to USM):** If efficacy data collected after study treatment discontinuation are available (retrieved drop-out), then the retrieved drop-out data will be excluded and missing data after study treatment discontinuation will be imputed via multiple imputation method using the MAR assumption.

The multiple imputations will be carried out on the weekly mean pain score. Details on multiple imputation can be found in Section 5 of this document.

The primary objective will be achieved if the EMA401 100 mg b.i.d. dose is statistically significant versus placebo in terms of the primary efficacy variable after multiplicity adjustment. To preserve the family-wise error rate at 2.5% level when comparing the EMA401 100 mg b.i.d. dose versus placebo on the primary and key secondary endpoints (see Section 2.6), statistical testing will be carried out using the following sequentially rejective, weighted Bonferroni-type test using the graphical approach (Bretz et al 2009) mentioned in Figure 2-1.

Figure 2-1 Sequentially rejective, weighted Bonferroni type test using the graphical approach

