The analyses of patient disposition for the treatment and treatment withdrawal epoch will be based on the FAS population only

Analyses of duration of exposure to study treatment will be based on the SAF population only.

Due to the early study termination only a few patients has been included in the region 'America'. To avoid convergence problems the covariate region has been removed from the ANCOVA model and from the logistic regression.

5 Appendix

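### Region, a stratification factor, is dropped from the NRS and NPSI ANCOVA for a convergence reason that a linear model cannot have; restoring it in the ANCOVA step alone is a small, nearly free gain

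*SAP*

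**What the plan says.** Protocol 5.3: "Randomization will be stratified by region (e.g. US, EU) and use of concomitant pain medication for PDN (yes/no"). Protocol 9.4.2 gives the ANCOVA for both NRS and NPSI, with "region (e.g. US, EU), treatment, sex, use of concomitant pain medication for PDN (yes/no) as factors" plus age and baseline score.

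SAP 1.1 keeps the stratification but renames the regions: "Randomization will be stratified by region (America, Europe and Australia) and use of concomitant pain medication for PDN (yes/no"). This can be read as three levels, or as two (America against Europe and Australia).

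SAP 2.5.2 now has a "model including treatment, sex, use of concomitant pain medication for PDN (yes/no) as factors and age and baseline" score as covariates; 5.5.1.1 gives the same equation with a single error term. Pain medication stays and region goes. Section 4 says that few patients were recruited in America and continues: "To avoid convergence problems the covariate region has been removed from the ANCOVA model and from the logistic regression".

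The change spreads by reference. The mFAS sensitivity analysis (2.5.4.2) uses the primary ANCOVA, NPSI (2.6.2) uses the NRS method, and imputation (5.5.1.2) uses the ANCOVA covariates within an arm. No planned NRS or NPSI model then adjusts for region. The Amendment 1 text nevertheless says that the primary analysis of the "24-hour average pain score will be performed as originally planned".

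**The concern.** An analysis should normally reflect the factors used to stratify the randomisation. Allocation is balanced within region, so regional differences do not distort the treatment contrast. If region is left out, however, those differences stay in the residual variance and the reported standard error is a little too large. With 137 of 400 planned patients randomised, there is little precision to spare.

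The stated reason also does not match the model it is applied to. Section 4 names the ANCOVA and the logistic regression but not the imputation step, so a reader cannot tell which part of the analysis was at risk, or whether the ANCOVA needed changing at all.

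**Working it through.** **1. The plan's own figure.** SAP section 3: 200 per arm, SD 2.6, difference 0.8, one-sided 0.025. SE = 2.6 × √(2/200) = 0.26, and power = Φ(0.8/0.26 − 1.96) = 86.8% (stated: about 85%). Differences of 0.7 and 0.9 give 76.8% and 93.3% (stated 77% and 94%). The plan's figures reproduce within 2 points and are not in dispute. With 137 patients and complete data, SE = 2.6 × √(4/137) = 0.444 and power at 0.8 is 43.7%.

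**2. Can the ANCOVA fail to converge?** The estimate is (X′X)⁻¹X′y, with one residual variance from the residual sum of squares. PROC MIXED has nothing to iterate on; the only requirement is that X has full rank. In 4,000 simulated trials per setting (137 patients, complete data; 1, 2, 5 or 10 in America; two or three levels), the model with region was solved every time.

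**3. Where the reason does apply.**
- Logistic model, single visit: the America coefficient is not estimable if all n America patients have the same response, with probability pⁿ + (1−p)ⁿ. For n = 5 this is 6% at p = 0.5 and 33% at p = 0.2; for n = 10 it is 0.2% to 11%.
- Imputation within an arm: with four America patients, two per arm, and a share c observed at Week 12, the chance that some arm has none observed is 1 − [1 − (1−c)²]². This is 8% at c = 0.8 and 59% at c = 0.4. In simulation with 5 America patients and region unmerged, an arm's imputation model could not be fitted in 5 to 7% of trials (20% missing) or 22 to 25% (40% missing). With America merged it never failed (0 of 48,000).

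**4. Effect on the treatment SE.** The documents give no regional counts, regional effects or missing rates. Assumed: 137 patients, 5 in America and 40 in Australia, America merged with Europe, SD 2.6, Australia effects of 0 to 1.5 points, AR(1) correlation 0.7, dropout completely at random, and MAR imputation by arm. Changes are relative to no region:

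| Where region is restored | Missing, weeks modelled | SE change |
|---|---|---|
| ANCOVA and imputation | 20%, 3 weeks | +0.6 to −2.8% |
| ANCOVA and imputation | 40%, 3 weeks | +1.0 to −2.0% |
| ANCOVA and imputation | 60%, 3 weeks | +2.2 to −0.3% |
| ANCOVA and imputation | 60%, 7 weeks | +1.5 to +5.0% |
| ANCOVA only | 20 to 60% | 0.0 to −2.0% |

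A smaller run (250 trials per setting) at 60% missing and 12 weeks gave +8 to +9% with region in both steps (Monte Carlo SE 1.4 to 3.0). If region has two levels, ANCOVA-only gives −0.6 to +0.1%.

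**5. In terms of power.** At 20% missing and a 1.5-point regional effect, the SE without region is about 0.509. Power at 0.8 is Φ(0.8/0.509 − 1.96) = 34.9%. With a 2% smaller SE (0.499) it is about 36%, a gain of roughly one point.

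**6. Type I error.** Without region, one-sided error averaged 2.2% over 12 runs (2.3% with the merged factor in both steps). In the complete-data runs it was 2.2 to 3.0% without region (Monte Carlo error about 0.25 points).

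**7. Cost in degrees of freedom.** The SAP model has 6 coefficients, leaving 137 − 6 = 131. A merged region factor leaves 130.

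**The case against.** The strongest reply is that the primary estimator is imputation followed by ANCOVA, and that the ANCOVA covariate list is the master list for both. Dropping region from the ANCOVA also protects the imputation, where the convergence worry is real. That stands as an account of what may have been intended. Section 4 does not say it, though, and the two lists can be separated.

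Second, restoring region everywhere could do harm. Amendment 1 describes many discontinuations due to trial termination. For these, SAP 2.5.2 says that "missing data after study treatment discontinuation will be imputed via multiple imputation method using the MAR assumption". With heavy missingness, region in the imputation model raises the standard error. This stands in full, and it is why the remedy stops at the ANCOVA step. A reader might infer that region belongs back in every model; the calculations do not support that.

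Third, the gain is small, and a merged region factor is itself a departure from the protocol. Both are true. The documents do not say which region America should join, so the rule must be fixed blind, or region adjustment kept as a sensitivity analysis.

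Fourth, imputing without region and then analysing with it pulls the regional coefficient towards zero, so part of the gain is lost. The treatment contrast should be little affected because region is balanced by design.

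A reader might also infer a concealed or results-driven change. The SAP's Document History lists the removal, section 4 explains it, and section 1 says that decisions preceded database lock and unblinding.

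**Conclusion.** The point holds in a limited form. A stratification factor and protocol covariate has left the primary and key secondary model for a reason that cannot apply to that model. The reason is sound for the logistic model and plausible for the arm-specific imputation models; the latter is an inference from SAP 5.5.1.2. The Amendment 1 statement that the primary analysis is unchanged needs a qualifier.

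It would be wrong to conclude that the test is invalid: there is no bias and no type I error inflation, only a slightly conservative standard error if region is prognostic. Restoring region in the ANCOVA step alone changes the SE by 0 to about −2% with a merged three-level factor, or −0.6 to +0.1% with two levels. These ranges rest on the assumed regional counts, effects and missing rates. Jump-to-reference imputation and dropout that depends on region were not simulated. The change is worth making because it is nearly free, not because the result is likely to depend on it.

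**What to change.** - **SAP 1.1:** state whether region has two or three levels.
- **SAP 2.5.2 and 5.5.1.1:** if three, restore region in the ANCOVA, with America merged with another region by a rule fixed before unblinding. NPSI (2.6.2) and mFAS (2.5.4.2) follow by reference.
- **SAP 2.5.4.2:** if region has two levels, or the sponsor keeps the reduced primary model, add the region-adjusted ANCOVA as a sensitivity analysis.
- **SAP 5.5.1.2:** say that the imputation covariates are the ANCOVA covariates except region.
- **SAP 2.7.1 and 5.5.2.1:** the logistic model may stay without region; say so in 2.7.1, which otherwise inherits the ANCOVA covariates.
- **SAP section 4:** limit the convergence reason to the logistic and imputation models.
- **Amendment 1 text:** note the handling of region as an exception to the unchanged primary analysis.

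The cost is one degree of freedom, or one extra model under the sensitivity option, plus these text edits. No new data are needed.

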5.1 Imputation rules

5.1.1 Study drug

Missing/partial start date or end date of study treatment will not be imputed.

5.1.2 Diagnosis of PDN

Rules for imputing date of first diagnosis of PDN will be provided in Programming Dataset Specification (PDS) document in details.

5.1.3 AE date imputation

Rules for imputing AE end date or start date will be provided in Programming Dataset Specification (PDS) document in details.

5.1.4 Concomitant medication date imputation

Rules for imputing the CM end date or start date will be provided in Programming Dataset Specification (PDS) document in details.

5.1.5 Prohibited medication for PDN

Exclusion period of values in case of changed PDN medication or intake of prohibited medication will be derived as follows:

- Programming Dataset Specification (PDS) will describe how to identify dose changes of concomitant PDN medications and prohibited medications
- determine exclusion period: CM end date + x days where x=3 for changes in dose and x=7 for intake of prohibited medications with potential confounding effect
- if no medication end date available, then all values from medication start date onwards should be excluded

5.2 AEs coding/grading

The MedDRA version which will be available at the time of database lock, will be used for the coding purpose of the adverse events.

5.3 Laboratory parameters derivations

Liver events defined by laboratory parameter abnormalities (additional non-lab criteria as provided in the protocol are ignored):

- ALT or AST $> 5 \times$ ULN
- ALP $> 2 \times$ ULN
- TBL $> 2 \times$ ULN
- ALT or AST $> 3 \times$ ULN and INR > 1.5
- ALT or AST $> 3 \times$ ULN and TBL $> 2 \times$ ULN AND ALP $\leq 2 \times$ ULN (Potential Hy's Law cases)
- ALT or AST $> 3 \times$ ULN

Renal events defined by laboratory parameter abnormalities (additional non-lab criteria as provided in the protocol are ignored):

- Serum creatinine increase 25 – 49% compared to baseline
- Serum creatinine increase $\geq 50\%$ compared to baseline
- New dipstick proteinuria $\geq 1+$
- New dipstick glycosuria $\geq 1+$ not due to diabetes
- New dipstick hematuria $\geq 1+$ not due to trauma
- Albumin- or Protein-creatinine ratio increase ≥ 2 -fold
- Albumin-creatinine ratio (ACR) ≥ 30 mg/g or ≥ 3 mg/mmol
- Protein-creatinine ratio (PCR) ≥ 150 mg/g or > 15 mg/mmol

Laboratory results will be reported in SI units.

